### **Study Overview and Design**

This is a single-center, randomized, factorial pilot trial at Michigan Medicine (Ann Arbor MI, USA). Approval was obtained from the University of Michigan Medical School Institutional Review Board (HUM00165251), and the trial has been registered at [www.clinicaltrials.gov](http://www.clinicaltrials.gov) (NCT04007523). This protocol is also compliant with the Consolidated Standards of Reporting Trials (CONSORT) extension for pilot and feasibility trials and the Standard Protocol Items: Recommendations for Interventional Trials (SPIRIT) Guidelines. Lastly, all study team members are certified in Good Clinical Practice.

After enrollment, patients (n=60) will be allocated (1:1:1:1), via block-randomization, stratified by gender, to one of four groups: usual care (n=15), HELP-based paging system (n=15), family-based paging system (n=15), or both HELP- and family-based paging system (n=15) (Figure 1). The randomization code will be created by the biostatistician (AT) and concealed from the rest of the research team. On the morning of surgery, allocation assignments will be delivered via sequentially numbered, opaque, sealed envelopes to unblinded research team members who will initiate arm-specific operations. The support systems will consist of automated pager alerts to the HELP program and/or family members and caretakers, depending on group allocation, for providing additional delirium evaluation and therapeutic prevention activities (see Interventions – Clinical Decision Support Paging System). Family members in the intervention group will also be provided with preoperative education on delirium and

training in the Family Confusion Assessment Method (FAM-CAM) instrument.

Although it will not be possible to blind patients and family members to family-based interventions, study team members will remain blinded to group allocation during daily assessments. Study flow is illustrated in Figure 1.

**Figure 1.** CONSORT study flow diagram. HELP = Hospital Elder Life program; CAM = Confusion

Assessment Method, LTAC = Long-Term Acute Care

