## **Statistical Analysis**

### *Sample Size and Power*

Given its fluctuating and recurrent nature, delirium presence will be primarily assessed over time with logistic generalized estimating equation models as we have done previously. In brief, time and group will serve as fixed factors, and a group by time interaction term will be included. Interaction terms will be removed from models if no significant interaction effect is observed. These models allow for longitudinal data analysis in the setting of incomplete and missing data. Group models will be constructed individually with the control group serving as a reference. Power calculations were then conducted with generalized estimating equations for the time-averaged difference between two groups (i.e., control group and intervention group, either HELP- or family-based support) in a repeated-measures design with the binary outcome of delirium. Accounting for six equally spaced measurements (twice daily delirium assessments for

the first three postoperative days), with an autoregressive correlation structure (baseline correlation 0.3) and linear missing data structure, a total sample size of 60 patients (n=30 in each intervention group) will provide >80% power to detect a difference in proportions of 15% (approximate Cohen's effect size difference of 0.9) for experiencing an episode of delirium between groups (assuming a baseline proportion of 20% in the control group) with  $\alpha=0.05$ . Power analysis was conducted using PASS 16 (PASS 2019 Power Analysis and Sample Size Software [2019]. NCSS, LLC. Kaysville, Utah, USA, [ncss.com/software/pass](http://ncss.com/software/pass)). As an exploratory analysis, the interaction between HELP- and family-based support groups will be assessed using a generalized estimating equations model.

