Considerable limitations are also worth discussion. The statistical powering strategy crucially assumes there is no interaction between the interventions (e.g., HELP- and family-based support), which may not be the case. However, this pilot phase will help generate effect size and feasibility data for refining future protocols and power calculations. Next, both HELP officials and family members may be subject to the Hawthorne effect. That is, individuals may modify their behavior under study conditions. Both HELP officials and family members may rigorously perform study protocols knowing that performance is being monitored. As such, protocol effectiveness will likely decrease in non-research settings. For the HELP program, performance measures will be compared to historical controls (2018 HELP records) to mitigate this effect. Family members of patients not randomized to family-based support interventions may still elect to spend more time with patients after learning about the trial and proceeding with enrollment. To assess for latent family support in the control groups, the research team will ask family members about time and activities with patients for comparisons to structured family-based support allocation groups. This will be assessed on the afternoon of postoperative day three, at the end of the inpatient study window, to avoid inadvertent introduction of study-related family support interventions. Additionally, while family members will receive basic training and education on FAM-CAM administration, they will not receive rigorous training for assessing reliability or accuracy. Such training could be pursued in a follow-up trial. Lastly, only patients with family members and/or caretakers – who will be available for the first three days of hospitalization – will be eligible for the trial. Thus, patients without such social support will be ineligible. These eligibility criteria thus exclude a group of

patients who may be particularly vulnerable to delirium (i.e., less social support) and reduce trial pragmatism.

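### The stated >80% power assumes a 20% delirium rate across a 30-patient comparator half, of whom 15 receive the other intervention; if both systems work as powered, power is about 67-77%, or about 50% if their benefits overlap

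*Combined protocol and SAP*

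**What the plan says.** Under Study Overview and Design, patients are allocated 1:1:1:1 to "usual care (n=15), HELP-based paging system (n=15), family-based paging system (n=15), or both HELP- and family-based paging system (n=15").

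Under Sample Size and Power, the calculation is for a time-averaged difference in a binary outcome between two groups, described as "control group and intervention group, either HELP- or family-based support". It states that "a total sample size of 60 patients (n=30 in each intervention group) will provide >80% power to detect a difference in proportions of 15" percentage points, "assuming a baseline proportion of 20% in the control group", at alpha 0.05. The other inputs are "Accounting for six equally spaced measurements", "with an autoregressive correlation structure (baseline correlation 0.3) and linear missing data structure" and an "approximate Cohen's effect size difference of 0.9". The same section says that each group model is to be built separately, with the control group as reference.

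Under Strengths and Limitations, the plan concedes: "The statistical powering strategy crucially assumes there is no interaction between the interventions". It does not say on which scale, and it says nothing about what the other intervention does to the comparator's delirium rate.

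**The concern.** Thirty patients on each side, using all 60, can be obtained only by pooling arms. For HELP, the 30 patients without it are 15 on usual care and 15 on the family system; for the family system, they are 15 on usual care and 15 on HELP. If usual care has 20% delirium and the other system also prevents delirium, the pooled comparator lies below 20%. The absolute difference at the margin then shrinks and events become scarcer. The disclosed no-interaction assumption does not cover this, because the comparator rate falls even when the two effects do not interact.

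Delirium is the primary outcome and its model is the primary inferential analysis. A power figure that holds only when the other system does little gives the wrong background for reading a non-significant result, and could carry into the sample size of the follow-on trial.

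**Working it through.** **Inputs from the plan.** 15 per arm; 30 vs 30; 20% vs 5%; six assessments; AR(1) correlation 0.3; alpha 0.05. **Assumptions.** Two-sided test (sidedness is not stated); complete data at first, since the amount of missingness is not given.

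**Formula.** The variance of a patient's mean over six assessments is p(1-p) x f, with f = [1 + (2/6) x sum over k = 1 to 5 of (6-k) x 0.3^k] / 6 = [1 + (2/6) x 1.9596] / 6 = 0.2755. Power = Phi(effect/SE - 1.96).
- Risk difference: SE = sqrt{(f/n) [p0(1-p0) + p1(1-p1)]}.
- Logit: SE = sqrt{(f/n) [1/(p0(1-p0)) + 1/(p1(1-p1))]}.

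**1. The plan's own figure, 20% vs 5%, n = 30 per side.**
- Logit: 1.558 / 0.501, power 88%.
- Risk difference: 0.150 / 0.0437, power 93%.
- Simulation of AR(1) binary data: 92-93%.
- The stated effect size also fits: 1.558 x sqrt(3)/pi = 0.86.

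So >80% reproduces.

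**2. Both systems lower 20% to 5%, no interaction on the logit scale.**
- Odds in the combined arm = (0.05/0.95)^2 / 0.25 = 0.0111, so the rate is 1.1%.
- Arms: 20%, 5%, 5%, 1.1%.
- Margins: (20 + 5)/2 = 12.5% vs (5 + 1.1)/2 = 3.05%.
- Logit: 1.514 / 0.628, power 67%.
- Risk difference: 0.0945 / 0.0357, power 75%. With within-arm variances the SE is 0.0349 and power is 77%.
- A main-effects logistic model adjusting for the other factor gives about 69-70%; simulation gives 71-75%.

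**3. Both systems lower 20% to 5%, combined arm stays at 5% (full overlap).**
- Margins: 12.5% vs 5%.
- Logit: 0.9985 / 0.527, power 47%.
- Risk difference: 0.075 / 0.0380, power 51% (52% with within-arm variances).
- Simulation: 46-47%.

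**4. How strong must the other system be?** The system under test lowers 20% to 5%, with no interaction on the logit scale.
- Other system alone gives 15%: margins 17.5% vs 4.3%; power 83% (logit), 89% (risk difference).
- Other system alone gives 12.5%: combined odds = (0.125/0.875)(0.05/0.95)/0.25 = 0.0301, rate 2.9%; margins 16.25% vs 3.96%; logit 1.549 / 0.556, power about 80%; risk difference 87%.

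**5. Missing assessments.** Suppose missingness rises linearly from 0% to 30% at the last assessment, through dropout (an assumed amount). A patient with m assessments contributes (0.7m + 0.6)/1.3 effective observations, so the average is 0.70 x 3.692 + 0.06 x (3.154 + 2.615 + 2.077 + 1.538 + 1.000) = 3.208. With 1/3.208 in place of f, power is 83-90% for step 1, 62-70% for step 2 and 43-46% for step 3.

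**6. If the control group means the usual-care arm and the comparison is with one single arm.** With n = 15 per side at 20% vs 5%, logit 1.558 / 0.708 gives 59% and risk difference 0.150 / 0.0617 gives 68%.

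**The case against.** The best reply is that a 30-patient control group in this design can only be the margin, so the 20% is the margin rate. The power then holds for both comparisons. With no interaction on the logit scale, margins of 20% and 5% require about 31.7% under usual care, 8.3% in each single arm and 1.7% in the combined arm; simulation with 32%, 8%, 8% and 2% gives about 91%. The Introduction quotes 20-50% delirium in older surgical patients, so 32% is not implausible. This stands as a possible reading. Against it, the ethics table describes controls as receiving ordinary care, and no usual-care rate near 32% appears anywhere in the plan. The documents do not settle the matter.

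A reader might therefore infer that the stated power is an arithmetic error, or that it cannot hold for both interventions. Neither is supported: the arithmetic is right for its inputs, and the second claim depends on reading 20% as the usual-care rate. Nor does the plan predict that each system will cut 20% to 5%. The 15 points is a detectable difference, and step 4 shows that a modest effect of the other system does little harm. It is also tempting to argue that no interaction would put the combined arm at 20 - 15 - 15 = -10%. The plan names no scale and its model is logistic, where the combined arm is a valid 1.1%.

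Usual care (15) against all HELP patients (30) would give about 81-89%, but it uses 45 patients rather than 60 and mixes in the family effect.

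Finally, this is a pilot. The plan already calls its no-interaction assumption crucial and open to doubt. Under Dissemination, moving to a larger trial depends on HELP practice and family feasibility, not on a significant delirium result. That limits the severity. It does not remove the gap, because step 2 grants no interaction and still falls short of 80%.

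**Conclusion.** The point holds in a conditional form. The >80% is correct if the entire comparator half has 20% delirium. If 20% is the usual-care rate, that is so only when the other system has little effect. Under two equally effective systems, power for each is about 67-77% without interaction on the logit scale, and about 47-52% with full overlap. These figures rest on a two-sided 0.05 test, AR(1) correlation 0.3 and complete data; missing assessments lower them. Severity is moderate: a stated power figure needs its conditions spelled out, and the design itself is not at fault.

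**What to change.** In Sample Size and Power:
- State whether 20% is the usual-care rate or the average of the non-intervention half. If it is the latter, give the implied usual-care rate of about 32%.
- If it is the usual-care rate, restate the power along these lines: *>80% for one intervention if the other has little or no effect on delirium; about 67-77% for each if both reduce 20% to 5% without interaction on the logit scale; about 50% if their benefits fully overlap (complete data; lower with missing assessments).*
- State that the powered analysis is the factorial-margin comparison using all 60 patients. Reconcile this with the sentence on separate group models against the control group, since usual care against one single arm (15 vs 15) has only about 59-68% power.

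In Strengths and Limitations, keep the no-interaction assumption, which the margin comparison still needs. Add that the stated power also assumes the other intervention does not materially lower the comparator half's delirium rate.

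The cost is wording only, with no extra patients; the downside is a less favourable stated power.

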## INTRODUCTION

Delirium is a distressing and common surgical complication, affecting approximately 20-50% of older surgical patients. Postoperative delirium is associated with increased mortality, cognitive and functional decline, and healthcare resource utilization. Of the diverse prevention strategies that have been tested with variable success, one notable proactive patient-care program, the Hospital Elder Life Program (HELP), has been shown to reduce delirium incidence through social and behavioral interventions (e.g., mealtime assistance, support with visual/hearing aids). However, substantial resources are needed for program sustainment, and delirium still persists in high-risk patients. In 2018, we found that <50% of surgical patients ≥70 years old at Michigan Medicine were officially enrolled in the program by the end of the second postoperative day. Furthermore, the average length of cumulative therapeutic activity was only 10 minutes across the first three postoperative days. This is pertinent given that the peak incidence of postoperative delirium occurs within the first 48 hours. As such, complementary strategies that improve patient triage and support may lead to earlier identification and therapeutic intervention for high-risk patients.

Clinical decision support systems can serve as a candidate strategy for mitigating delirium risk. Such systems provide targeted patient- and disease-specific information, presented in a timely manner, for improving healthcare quality. In the context of delirium, automated pages could be sent to supportive healthcare services, such as HELP, along with family members and caretakers, with alerts and targeted recommendations. An alert page could be sent to HELP program officials on the first

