## **Outcomes**

The primary outcome of this pilot trial will be the presence of delirium, defined by a positive long-form Confusion Assessment Method (CAM) screening. To complement CAM screening, delirium will also be assessed each day via validated chart review method. The following secondary outcomes will also be collected and analyzed: delirium severity (long-form CAM severity scale), new symptoms of depression or anxiety (using the Hospitalized Anxiety and Depression Scale, HADS), falls (proportion, %), length of hospital stay (days), discharge disposition (e.g., home, long-term care facility), delayed discharge due to cognitive impairment (proportion, %), incidence of any new non-surgical site infection (%), incidence of new multidrug resistant organism colonization (%), and mortality (%). Exploratory outcomes will include the incidence of positive FAM-CAM assessments (%) 30 days post-discharge, PROMIS Cognitive Function Abilities (Short Form 4a), 36-Item Short Form Survey, and 30-day readmission rates.

**Protocol Fidelity Measures:** Lastly, protocol fidelity measures will be reported for both HELP- and family-based interventions. HELP-based measures include the following: total therapeutic time spent with HELP staff during the first three postoperative days, proportion of participants visited and enrolled by HELP (%), and time to initial HELP evaluation. For family-based interventions, the following measures will be reported: cumulative time family members spent with patients, proportion of daily tasks (e.g., assistance with glasses/hearing aids, handwashing), successfully completed, length of time spent on stimulating activity, and overall agreement of the FAM-CAM with interview-rated CAM assessments.

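### The power above 80% is calculated for the proportion CAM-positive per assessment, but the sentence attaches it to patients having an episode of delirium, for which power is well below 80%

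*Combined protocol and SAP*

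**What the plan says.** In the combined protocol and SAP, Sample Size and Power says that power was calculated "with generalized estimating equations for the time-averaged difference between two groups" on a binary repeated measure with six equally spaced assessments, "with an autoregressive correlation structure (baseline correlation 0.3) and linear missing data structure". With 60 patients, 30 per group, the trial "will provide >80% power to detect a difference in proportions of 15" percent, described as an approximate Cohen "effect size difference of 0.9". The same sentence says what the difference refers to: "for experiencing an episode of delirium between groups (assuming a baseline proportion of 20% in the control group").

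Under Outcomes, the primary outcome "will be the presence of delirium, defined by a positive long-form Confusion Assessment Method (CAM) screening". That sentence alone does not say whether the unit is the assessment or the patient. The only background rate of delirium in the document is in the Introduction, "affecting approximately 20-50% of older surgical patients", and it counts patients.

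**The concern.** A time-averaged GEE contrast takes as its input the proportion positive at a typical assessment. An episode is something that a patient has, so a proportion with an episode counts patients positive at least once. The two can differ by a factor of several when each patient is assessed six times. The sentence gives the power for the first quantity and names the second, and its 20% coincides with the lower end of a range that counts patients. A reader could take away that 30 patients per group give more than 80% power for a fall from 20% to 5% of patients with delirium.

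The stakes are modest. Strengths and Limitations says "this pilot phase will help generate effect size and feasibility data for refining future protocols and power calculations", so the scale of the assumed rate and effect should be clear to whoever plans the next trial. The six CAM results per patient allow both rates to be computed at the end.

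**Working it through.** **Inputs from Sample Size and Power:** 30 versus 30; six assessments; AR(1) correlation 0.3; alpha 0.05; control 20%; difference 15 points.

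**Assumptions:** two-sided test; a reduction to 5%; prevalence constant over time; complete data unless stated.

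**1. Direction of effect.** For 20% versus 5% the odds ratio is (0.20/0.80)/(0.05/0.95) = 4.75. Then ln 4.75 × √3/π = 1.558 × 0.551 = 0.86, which fits the stated approximate 0.9. An increase to 35% would give 0.42. So 20% versus 5% is the scenario used.

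**2. The plan's own figure, per assessment.** Information per patient under AR(1) is (6 − 4 × 0.3)/1.3 = 3.692 effective observations.
- Log-odds scale: variance = (1/0.16 + 1/0.0475)/(30 × 3.692) = 0.2465; z = 1.558/√0.2465 = 3.14; power = Φ(3.14 − 1.96) = 88%.
- Difference scale: variance = (0.16 + 0.0475)/(30 × 3.692) = 0.001873; z = 0.15/√0.001873 = 3.47; power 93%.
- The plan gives the shape of the missing data (linear) but no rate. If the missing proportion rises from 0 at the first assessment to an assumed 50% at the last, with patients not returning once missing, information is 1 + (0.7/1.3) × (0.9 + 0.8 + 0.7 + 0.6 + 0.5) = 2.885. Power is then 79% (log-odds) and 87% (difference).

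The stated power above 80% therefore reproduces on this scale, and is marginal only on the log-odds scale at the 50% loss.

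**3. Patients with an episode, compared once per patient.** 20% versus 5%, 30 per group:

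| Test | Power |
|---|---|
| Fisher exact (enumerated) | 24% |
| Logit Wald | 37% |
| Pooled normal | 42% |
| Unpooled normal | 44% |
| Uncorrected chi-squared (enumerated) | 45% |

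For the pooled normal test, the null standard error is √(2 × 0.125 × 0.875/30) = 0.0854 and the alternative standard error is √(0.2075/30) = 0.0832. Power = Φ((0.15 − 1.96 × 0.0854)/0.0832) = Φ(−0.21) = 42%. A one-sided alpha of 0.05 would raise it only to 55%. For 80% power this test would need 76 per group.

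**4. The planned GEE, if 20% and 5% are patients ever positive over six assessments.** The per-assessment proportions must then be much smaller. Bounds on the probability of at least one positive, using only the single and pairwise probabilities implied by AR(1) 0.3, limit the control proportion to 0.0386-0.0618 and the intervention proportion to 0.0094-0.0129. The most favourable pair is 0.0618 versus 0.0094:
- Difference scale: variance = (0.0618 × 0.9382 + 0.0094 × 0.9906)/(30 × 3.692) = 0.000608; z = 0.0524/√0.000608 = 2.13; power 57%.
- Log-odds scale: power 45%.

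About 57% is thus a ceiling under these conditions (normal approximation). With a first-order Markov chain, which is an added assumption, the proportions are 0.0487 and 0.0113 and the formula gives 32-37%.

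**5. What 20% per assessment implies for patients.** Expected positives per patient: S1 = 6 × 0.20 = 1.2. The sum of pairwise joint probabilities is S2 = 15 × 0.04 + 0.16 × (5 × 0.3 + 4 × 0.09 + 3 × 0.027 + 2 × 0.0081 + 0.00243) = 0.9135. The lower bound on patients ever positive (Dawson-Sankoff) is (2/3) × 1.2 − (1/3) × 0.9135 = 49.5%, with all six assessments observed. The Markov assumption gives 62%.

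**The case against.** The strongest reply is that the section already fixes the scale. It says that delirium presence is assessed primarily over time because it fluctuates, names a time-averaged contrast, and lists six repeated binary measurements. On that text the per-assessment reading is the dominant one, and a single loose phrase does not undo it. This stands: the point concerns the label on the power, and the phrase remains wrong for the quantity that was powered.

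Three stronger readings do not stand.
- A reader might infer that the software result is an arithmetic error. It is not; step 2 reproduces it.
- A reader might infer a precise patient-level power, such as 20-40%. The value depends on the test, on the joint distribution of the six results and on how arms without events are handled. The steps above support only that it is well below 80%.
- A reader might infer that 20% per assessment contradicts the cited 20-50% of patients. The floor of 49.5% lies at the top of that range, and the trial recruits patients at high risk. Only the Markov value exceeds the range, and that model is not in the plan.

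It is also fair to say that future power calculations would use the pilot's observed rates rather than the assumed 20%, which limits the consequence.

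**Conclusion.** The power statement is mislabelled. It holds for 20% versus 5% CAM-positive per assessment (88-93% with complete data; 79-87% at an assumed 50% missing by the last assessment). It does not hold for 20% versus 5% of patients with an episode: 24-45% for a once-per-patient comparison, and at most about 57% for the GEE.

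These figures take the stated 30 versus 30 comparison as given and assume a two-sided alpha of 0.05. The GEE figures also assume AR(1) 0.3 and constant prevalence, and the 57% ceiling assumes complete data. The once-per-patient result needs no model for the repeated assessments. Severity is minor. The undeclared missing-data rate is a separate reporting gap on which this conclusion does not depend.

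**What to change.** In the sentence quoted above, replace the words about an episode of delirium with: in the time-averaged proportion CAM-positive per assessment between groups. Then add two statements:
- The trial's power for a 20% versus 5% difference in patients with at least one episode is well below 80%.
- The assumed 20% is per assessment. With AR(1) correlation 0.3 and all six assessments observed, it implies at least about 49.5% of control patients ever positive, at the top of the range cited in the Introduction.

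The cost is two or three sentences, with no change to sample size, conduct or, on the dominant reading, analysis.

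If patients with an episode were the intended outcome, the cost is higher. The claim of more than 80% should be withdrawn and the power restated for that outcome. The primary analysis should also be aligned with it, because a time-averaged GEE does not directly estimate a difference in patients ever positive.
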